5. PRIMARY AND SECONDARY ENDPOINTS

5.1. Primary Endpoint

- Glycemic efficacy of RZ358 as evaluated by the average daily percent time within a glucose target range of 70-180 mg/dL (3.9-10 mmol/L) by CGM
- Repeat-dose safety and tolerability of RZ358
- Repeat-dose pharmacokinetics of RZ358

5.2. Secondary Endpoints

- Average weekly incidence of hypoglycemia (< 70 mg/dL) by self-monitored blood glucose (SMBG)
- Average daily duration (min) and percent time with hypoglycemia at thresholds of <70, <60, and <50 mg/dL (3.9, 3.3, and 2.8 mmol/L, respectively) by CGM
- Average daily hypoglycemia incidence (event rate) at each of the specified glucose thresholds by CGM
- Average 8h overnight percent time in glucose target range of 70-180 mg/dL (3.9-10 mmol/L) by CGM
- Occurrence of hypoglycemia during a 12h fasting challenge.

5.3. Additional (Exploratory) Endpoints

- Average 8h overnight duration (min) and percent time with hypoglycemia at thresholds of <70, <60, and <50 mg/dL (3.9, 3.3, and 2.8 mmol/L, respectively) by CGM
- Average 8h overnight hypoglycemia incidence (event rate) at each of the specified glucose thresholds by CGM

- Average daily and 8h overnight area over and under the glucose curve (AUC, AOC) for each of the specified glucose thresholds by CGM
- Average glucose level between midnight and 8:00 AM (or nearest pre-breakfast time point) by CGM
- Average weekly hypoglycemia incidence (event rate) at each of the specified glucose thresholds by SMBG
- Intravenous or enteral nutritional (glucose/dextrose) supplementation
- Use of SoC or rescue medications for hypoglycemia (dextrose or other)
- Incidence of fasting blood glucose values >200, >250, and >300 mg/dL (>11.1, >13.9, and >16.6 mmol/L, respectively)
- PD Markers of RZ358 activity including fasting levels of glucose, insulin, c-peptide, glucagon, FFAs, and ketones (beta-hydroxybutarate).

6. ANALYSIS POPULATION AND TREATMENT GROUPS

6.1. Analysis Population

ITT Population: All patients who are enrolled into the study.

Safety Population: All patients enrolled in the study who receive at least one dose of study drug.

Per protocol Population: All patients who receive at least 4 weeks of study drug (2 bi-weekly doses), with no major protocol violations. A patient in the Per protocol population may be excluded from one or more specific efficacy analyses (i.e. SMBG-related endpoints or CGM-related endpoints), if they have a major protocol deviation affecting only that endpoint (e.g. non-compliance with SMBG only, or non-compliance with CGM only).

PK Population: All patients who receive study drug and have a sufficient number and quality (biologically plausible) of results.

6.2. Treatment Groups

The study will consist of up to 4 dose cohorts, which are to be enrolled independently and conducted sequentially, comprised of up to 6-8 patients per cohort to ensure each cohort includes at least 3 patients aged ≤ 10 years with hypoglycemia due to CHI.

In Cohorts 1, 2, and 3 the dose amount will be fixed during the entire 8-week Treatment Period, while in Cohort 4 there will be a scheduled bi-weekly dose-titration for the first 4 weeks, followed by a fixed dose amount thereafter for the remaining 4 weeks. (Refer [section 2.2](#), Table 1: Study Design/Cohort Dosing Regimens).

The cohorts will be labelled in the TLFs as Cohort 1 (3 mg/kg), Cohort 2 (6 mg/kg), Cohort 3 (9 mg/kg), Cohort 4 (Dose Escalation mg/kg), and RZ358 Total.

7. ANALYSIS METHODS AND REPORTING DESCRIPTION

7.1.1. Subject Disposition

Subject disposition will be summarized using frequency count and percentage by cohort and RZ358 Total, for number of subjects screened, number of subjects enrolled, number of subjects in the ITT population, number of subjects in the Safety populations, number of subjects in the Per protocol (PP) population, number of subjects in the PK population, number of subjects who completed the study treatment, number of subjects who completed the study, number of subjects who discontinued the study but completed the treatment and number of patients who discontinued from the study along with the reasons for discontinuation from the study.

A listing of subject's disposition will be presented to describe dates of completion or early withdrawal for each patient with the reason for early discontinuation, if applicable.

7.1.2. Demography and Baseline Characteristics

The demographic and baseline characteristics will include age (years), age group (2-6, 7-11, 12-17 and ≥ 18 years), gender, ethnicity, race, height (cm), weight (kg), and BMI (kg/m^2). These will be summarized by cohort and RZ358 Total, for the ITT Population and Per protocol (PP) Population.

Baseline CHI characteristics will include genetic type, CHI medication history, pancreatectomy, exocrine pancreatic insufficiency, repeat surgeries, tube feeding catheter, and type of nutrition and will be summarized by cohort and RZ358 Total, for ITT Population.

Descriptive statistics (n, mean, SD, minimum, median, and maximum) will be presented for continuous variables. Count and percentage will be presented for each class of the categorical variables.

All individual patient demographic and baseline characteristic data will be listed.

7.1.3. Medical and Surgical History

Medical and Surgical history will be summarized by system organ class (SOC) and preferred term (PT) using count and percentage by cohort and RZ358 Total, for the Safety Population. Patients will be counted only once at the PT, only once at the SOC, and only once at patient level for the counting of total number of patients with a medical history term. Counts will be presented in descending frequency unless otherwise specified. Medical history will be coded using MedDRA version 25.0 Mar 2022.

Listing of medical and surgical history will also be presented for Safety Population.

7.1.4. Prior and Concomitant Medications

Any medication other than study drug, either prescription drug or over the counter (OTC) will be treated as concomitant medication.

Prior Medications

For a patient in the Safety Population, prior medications will include any medication taken within 30 days of signing ICF but stopped prior to patient's first dose of Study Medication.

Concomitant Medications

Concomitant medications are defined as prescribed medications and over the counter (OTC) preparations, including herbal preparations and vitamins, other than Study Medication taken within 30 days of ICF and during the treatment and follow-up phase.

Prior and concomitant medication will be categorized by preferred Term and ATC level X class per World Health Organization Drug Dictionary (WHODRUG; Version Global B3 SEP2019) will be summarized by cohort and RZ358 Total, for the Safety Population. The count and percentage of patients using each medication will be displayed. Patients who taken the same medication (in terms of PT) more than once will be counted only once for that medication.

All prior and concomitant medications will be presented in a listing for the Safety Population.

7.1.5. Protocol Deviation

Protocol deviations will be identified and classified by ICH category 1 through 5 and as minor or major and Important Protocol Deviations (as defined by ICH) will be summarized using count and percentage by cohort and RZ358 Total, for the Safety Population. A listing of patients with protocol deviations will be presented.

Compliance will be check for CGM & SMBG and below definitions will be used for the same.

CGM (Continuous glucose monitoring)

Percent compliance of CGM data will be defined as $\geq 70\%$ data capture during the overall monitored time during the treatment period, including $\geq 70\%$ data capture during the efficacy evaluable period between last dose of study drug and the Day 14 EOT/Follow-up Visit.

$$CGM\ Compliance\ (%) = \frac{\text{Actual number of 5 minutes interval of CGM readings}}{\text{Expected number of 5 minutes interval of CGM readings}} \times 100$$

Subjects will be considered compliant if the % compliance is calculated to be $\geq 70\%$ by each of the above criteria and compliance rate will be summarized using descriptive statistics. Overall compliance will also be summarized using counts and percentages by categorizing it into compliant and non-compliant.

Note: Data capture is defined as available recordings in the 10-day sensor period.

SMBG (Self-Monitoring of Blood Glucose)

Percent compliance of SMBG data will be defined as $\geq 50\%$ data capture during the overall monitored time during the treatment period, including $\geq 75\%$ data capture during the efficacy evaluable period between the last dose of study drug and the Day 14 EOT/Follow-up Visit.

$$\text{SMBG Compliance (\%)} = \frac{\text{Actual number of SMBG readings}}{\text{Expected number of SMBG readings}} \times 100$$

Subjects will be considered compliant if the % compliance meets each of the above criteria, and compliance rate will be summarized using descriptive statistics. Overall compliance rate will be summarized using counts and percentages by categorizing it into compliant and non-compliant.

(b) (4)

7.1.6. Study Drug Exposure and Treatment Compliance

Duration of study drug exposure will be summarized by cohort using descriptive statistics (n, mean, SD, minimum, median, and maximum) for the Safety Population. For each subject, duration of study drug exposure (days) will be calculated as below:

$(\text{Date of last administration of study drug} + 14 \text{ Days}) - \text{Date of first administration of study drug} + 1$.

Compliance to the study drug will be calculated as:

$$\text{Treatment Compliance (\%)} = \frac{\text{Actual number of doses taken}}{\text{Total number of scheduled doses}} \times 100$$

Subjects will be considered compliant, if the % compliance is calculated at least 75% and have at least completed 4 weeks of study treatment. The compliance rate will be summarized by cohort using descriptive statistics (n, mean, SD, minimum, median, and maximum) for the Safety Population. Also,

overall compliance will be summarized by cohort using counts and percentages by categorizing it into compliant and non-compliant for the Safety Population. Separate listing will also be provided.

7.1.7. Efficacy Analysis

7.1.7.1. Primary Endpoint

A CGM system will be used to evaluate glycemic eligibility and efficacy endpoints for glycemic control. Several parameters to measure glycemic control by CGM will be evaluated over the 2-week End of Treatment period after the final dose, compared to baseline. The efficacy analysis will be conducted in the Intent-to-Treat (ITT), and Per-Protocol (PP) Populations.

The primary endpoint is the glycemic efficacy of RZ358 as evaluated by the average daily percent time within a glucose target range of 70-180 mg/dL (3.9-10 mmol/L) by CGM. The derivation of daily percent time within a glucose target range of 70-180 mg/dL (3.9-10 mmol/L) is presented in [section 4.1](#). The primary endpoint of actual and change from baseline values will be summarized by visit, cohort and RZ358 Total using descriptive statistics (n, Mean, SD, SE, Median, Minimum, Maximum, and 95% CI for Mean). Within cohort comparative analysis will be performed using paired t test by comparing each post baseline visits with baseline visit, p-value from the test will be reported and analysis will be performed using ITT and PP Populations. Corresponding mean (SD) plot will also be produced to illustrate the descriptive statistics as appropriate.

7.1.7.2. Secondary Endpoints

The secondary endpoints to measure glycemic control by CGM and SMBG will be evaluated, at each of the specified timepoints, compared to baseline. The analysis of CGM parameters and SMBG parameters will be evaluated over the 2-week End of Treatment period after the final dose, compared to baseline. The secondary endpoints analysis will be conducted in the Intent-to-Treat (ITT), and PP Populations. The following secondary endpoints include:

- Average weekly incidence of hypoglycemia (< 70 mg/dL) by self-monitored blood glucose (SMBG)
- Average daily duration (min) and percent time with hypoglycemia at thresholds of <70, <60, and <50 mg/dL (3.9, 3.3, and 2.8 mmol/L, respectively) by CGM
- Average daily hypoglycemia incidence (event rate) at each of the specified glucose thresholds by CGM
- Average 8h overnight percent time in glucose target range of 70-180 mg/dL (3.9-10 mmol/L) by CGM

The derivations of above secondary endpoints are presented in [section 4.1](#). The secondary endpoints of actual and change from baseline values will be summarized by visits, cohort and RZ358 Total using descriptive statistics (n, Mean, SD, SE, Median, Minimum, Maximum and 95% CI for Mean). Along with these, First Quartile (Q1) and Third Quartile (Q3) will also be presented for duration (min) parameters. Within cohort comparative analysis will be performed using paired t test by comparing each post baseline visits with baseline visit, p-value from the test will be reported and analysis will be performed using ITT and PP Populations. Corresponding mean (SD) plots will also be produced for parameters to illustrate the descriptive statistics as appropriate.

The secondary endpoints “Average daily Percent time with hypoglycemia at thresholds of <70, <60, and <50 mg/dL (3.9, 3.3, and 2.8 mmol/L, respectively) by CGM” and “Average weekly incidence of hypoglycemia (< 70, <60, <50 mg/dL) by self-monitored blood glucose” will also be summarized by the percent change from baseline by visit, cohort and RZ358 Total using descriptive statistics (n, Mean, SD, SE, Median, Minimum, Maximum and 95% CI for Mean). Within cohort comparative analysis will be performed using paired t test by comparing each post baseline visits with baseline visit, p-value from the test will be reported and analysis will be performed using ITT and PP Populations.

Occurrence of hypoglycemia during a 12h fasting challenge:

- Time to termination of fast
- Glucose nadir during fast
- Percentage of patients able to complete a fast
- Ketone levels at the conclusion of fast

Above mentioned parameters i.e., Time to termination of fast, Glucose nadir during fast, and Ketone levels at the conclusion of fast will be summarized by visit, cohort and RZ358 Total using descriptive statistics (n, Mean, SD, SE, Median, Minimum, Maximum and 95% CI for Mean). Within cohort comparative analysis will be performed using paired t test by comparing week 7 visit with baseline visit, p-value from the test will be reported and analysis will be performed using Intent-to-Treat (ITT), and PP Populations.

Also, Percentage of patients able to complete a fast will be summarized using frequency count and percentage by visit, cohort, and RZ358 Total. Within cohort comparison of proportions will be performed using McNemar’s test by comparing week 7 visit with baseline visit, p-value from the test will be reported and analysis will be performed using Intent-to-Treat (ITT), and PP Populations.

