4.3 Inclusion Criteria

Patients who meet ALL of the following criteria are eligible to participate in the study.

1. Provide written informed consent and, as applicable, assent, before any study-specific procedures are performed.
2. At Screening, aged ≥ 12 years and ≤ 45 years.
3. An established clinical diagnosis, with or without a genetic diagnosis, of congenital hyperinsulinism.
4. Patient is currently receiving SOC medications (e.g., diazoxide, lanreotide, sirolimus, pasireotide, or octreotide) and/or nutritional supplementation for CHI, with at least 2 months of stable treatment; OR is not on treatment at the time of Screening.
5. Glucose values <70 mg/dL (3.9 mmol/L) for $\geq 4\%$ of the overall monitored CGM time with at least 3 severe hypoglycemia events by CGM threshold of <50 mg/dL (2.8 mmol/L) during the last 7 days of a 10-day Screening CGM evaluation period.

(b) (4)

AND:

Experiencing ≥ 3 hypoglycemia events (<70 mg/dL) per week by SMBG and/or according to the Investigator's evaluation.

6. Hepatic ultrasound at Screening without clinically significant findings, including clinically significant gallstones as judged by the Investigator (e.g. large size, obstructive, biliary colic or LFT abnormalities exceeding protocol thresholds), or evidence of peliosis hepatitis.

7. For female patients of childbearing potential, a negative serum or urine pregnancy test within 7 days before dosing;
 - Females of childbearing potential are defined as fertile following menarche and until becoming postmenopausal or permanently sterile. (Postmenopausal is defined as absence of vaginal bleeding or spotting for at least 1 year. Permanently sterile is defined as having had a hysterectomy, bilateral salpingectomy, or bilateral oophorectomy.)
 8. For female patients of childbearing potential, a willingness to use highly effective* contraceptive measures adequate to prevent a new pregnancy for the duration of the study, including for at least 105 days after receiving the last dose of study drug. For women with reproductive potential who use a hormonal method of contraception, concurrent use of a second (barrier) method is recommended.

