3. DATA ANALYSIS CONSIDERATIONS

The statistical analyses will be performed by Quartesian Clinical Research, using SAS Version 9.3 (or higher). All Tables, Listings and Figures (TLFs) will be produced in landscape format. In general, all data will be listed by the patient, cohort, and visit/timepoint, but not limited only to these variables. The number of variables presented in each listing can vary. Please refer to Mock tables, listings, and figures.

Data will be summarized by cohort and by RZ358 pooled treatment. The total number of patients in the study group (N) under the stated population will be displayed in the cohort header of summary tables.

Data will be summarized using descriptive statistics for continuous variables. Unless otherwise stated, descriptive statistics will include Number of patients (n), Mean, Standard Deviation (SD), Standard Error (SE), Minimum, Median, Maximum, and confidence interval (for efficacy parameters only). First Quartile (Q1) and Third Quartile (Q3) will also be included for duration (absolute time) parameters. Area over the curve (AOC) and area under the curve (AUC) of glucose will also include coefficient of variation (CV %), Geometric Mean, Geometric CV (%). In case of n=1, where n

indicates the number of evaluable patients at the particular time point, only n, mean, minimum and maximum will be displayed. The statistic “Missing” will also be evaluated by enumerating the number of missing entries/patients, if any at that visit, and presented as a summary statistic only for the available time points.

In summary tables of categorical variables, counts and percentages will be used. The count [n] indicates the actual number of patients with a particular value of a variable or event, which should always be less than or equal to the total number of patients in the respective cohort [N].

Decimal Precision Convention: The minimum and maximum statistics will be presented to the same number of decimal places as the raw data. The mean, median, Q1, Q3, Confidence interval (CI) for mean and proportion will be presented to one more decimal place than the raw data, whereas the standard deviation (SD), Standard Error (SE), coefficient of variation (CV %), Geometric Mean, and Geometric CV (%) will be presented to two more decimal places than the raw data.

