7.1.7.3. Exploratory Endpoints

The exploratory endpoints to measure glycemic control by CGM and SMBG will be evaluated, at each of the specified timepoints, compared to baseline. The analysis of CGM parameters and SMBG

parameters will be performed over the 2-week End of Treatment period after the final dose, compared to baseline. The exploratory endpoints analysis will be conducted in the PP and ITT Populations. The following exploratory endpoints include:

- Average 8h overnight duration (min) and percent time with hypoglycemia at thresholds of <70, <60, and <50 mg/dL (3.9, 3.3, and 2.8 mmol/L, respectively) by CGM
- Average 8h overnight hypoglycemia incidence (event rate) at each of the specified glucose thresholds by CGM
- Average daily and 8h overnight area over and under the glucose curve (AUC, AOC) for each of the specified glucose thresholds by CGM
- Average glucose level between midnight and 8:00 AM (or nearest pre-breakfast time point) by CGM
- Average weekly hypoglycemia incidence (event rate) at each of the specified glucose thresholds of <70, <60, and <50 mg/dL (3.9, 3.3, and 2.8 mmol/L, respectively) by SMBG

Additionally, Average weekly hyperglycemia incidence (event rate) at each of the specified glucose thresholds of >180, >250, and >300 mg/dL (10.0, 13.9 and 16.6 mmol/L, respectively) by SMBG

The derivations of above exploratory endpoints are presented in [section 4.1](#). The exploratory endpoints of actual and change from baseline values will be summarized by visit, cohort and RZ358 Total using descriptive statistics (n, Mean, SD, SE, Median, Minimum, Maximum and 95% CI for Mean). Along with these, First Quartile (Q1) and Third Quartile (Q3) will also be presented for duration (min) parameters. AOC and AUC of above glucose parameters will also be summarized by visit, cohort and RZ358 Total using descriptive statistics (n, Mean, SD, SE, CV (%), Geometric Mean, Geometric CV (%), Median, Minimum, Maximum and 95% CI for Geometric Mean). Within cohort comparative analysis will be performed using paired t test by comparing each post baseline visits with baseline visit, p-value from the test will be reported and analysis will be performed using ITT and PP Populations. Corresponding mean (SD) plots will also be produced for above endpoints to illustrate the descriptive statistics as appropriate.

Comparison of glycemic efficacy of RZ358 by CGM/SMBG endpoints

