The within cohort comparison of post baseline visits to baseline visit in glycemic efficacy of CGM/ SMBG endpoints over the 2-week End of Treatment period after the final dose will be analyzed using paired t-test and p-value from the test will be reported.

The null and alternative hypothesis are,

$$H_0 : \mu_d = 0 \quad \text{and} \quad H_1 : \mu_d \neq 0$$

Where, μ_d is the mean difference in glycemic efficacy of CGM/SMBG parameters within cohort.

The normality of the CGM/SMBG endpoints will be performed using Shapiro-Wilk Test. If the p -value from the test result is normal, that is, p -value ≥ 0.05 , then paired t-test will be used; otherwise, a non-parametric Wilcoxon Sign Rank Test will be used.

Additional endpoints

Listings will be presented for the following additional endpoints.

- Intravenous or enteral nutritional (glucose/dextrose) supplementation
- Use of SoC or rescue medications for hypoglycemia (dextrose or other)

Pharmacodynamic Biomarker Analyses

Blood samples will be collected at scheduled timepoints, throughout the treatment periods of the study to evaluate the PD effects of the study drug. The PD of RZ358 compared to baseline will be assessed by:

- Average levels of glucose, insulin, c-peptide, glucagon, FFAs, and ketones (beta-hydroxybutarate), at each of the specified collection timepoints.

The actual and change from baseline values of the above parameters will be summarized using descriptive statistics (n, Mean, SD, SE, Median, Minimum, Maximum and 95% CI for Mean) at each of the specified collection timepoints by visit, cohort and RZ358 Total for the PP population.

- Incidence of safety fasting blood glucose values >200 , >250 , and >300 mg/dL (>11.1 , >13.9 , and >16.6 mmol/L, respectively).

Incidence of safety fasting blood glucose values >200 , >250 , and >300 mg/dL (>11.1 , >13.9 , and >16.6 mmol/L, respectively) will be summarized using frequency count and percentage at each of the specified collection timepoints by visit, cohort and RZ358 Total for the PP population.

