7.1.7.4. Summary of Efficacy Endpoint Analysis Strategy

Endpoint	Statistical Method / Test	Analysis Population	Missing Data Imputation Approach	Parameters/Variables in the analysis (Stat. test/Model)	Analysis Time point
Primary Endpoint					
Glycemic efficacy of RZ358 as evaluated by the average daily percent time within a glucose target range of 70-180 mg/dL (3.9-10 mmol/L) by CGM	Descriptive statistics, Paired T-test (analyzing post baseline visits with baseline visit)	PP Population and ITT Population	No imputation	Average daily percent time, cohort	8 Weeks /EOT
Secondary Endpoint					
Average weekly incidence of hypoglycemia (< 70 mg/dL) by self-monitored blood glucose (SMBG)	Descriptive statistics, Paired T-test (analyzing post baseline visits with baseline visit)	PP Population and ITT Population	No imputation	Average weekly incidence, cohort	8 Weeks /EOT

Endpoint	Statistical Method / Test	Analysis Population	Missing Data Imputation Approach	Parameters/Variables in the analysis (Stat. test/Model)	Analysis Time point
Average daily duration (min) and percent time with hypoglycemia at thresholds of <70, <60, and <50 mg/dL (3.9, 3.3, and 2.8 mmol/L, respectively) by CGM	Descriptive statistics, Paired T-test (analyzing post baseline visits with baseline visit)	PP Population and ITT Population	No imputation	Average daily duration, Average daily percent time, cohort	8 Weeks /EOT
Average daily hypoglycemia incidence (event rate) at each of the specified glucose thresholds by CGM	Descriptive statistics, Paired T-test (analyzing post baseline visits with baseline visit)	PP Population and ITT Population	No imputation	Average daily hypoglycemia incidence, cohort	8 Weeks /EOT
Average 8h overnight percent time in glucose target range of 70-180 mg/dL (3.9-10 mmol/L) by CGM	Descriptive statistics, Paired T-test (analyzing post baseline visits with baseline visit)	PP Population and ITT Population	No imputation	Average 8h overnight percent time, cohort	8 Weeks /EOT

Endpoint	Statistical Method / Test	Analysis Population	Missing Data Imputation Approach	Parameters/Variables in the analysis (Stat. test/Model)	Analysis Time point
Occurrence of hypoglycemia during a 12h fasting challenge. (Percentage of patients able to complete a fast)	Count and percentage, Comparison of proportions using McNemar Test.	PP Population and ITT Population	No imputation	eCRF	Week 7

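### Mean individual percent change in SMBG events below 60 and below 50 mg/dL is undefined or unstable at zero or low baselines, and geometric statistics for AOC fail when a patient has no reading below threshold (minor)

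*SAP*

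**What the plan says.** **Percent change.** SAP section 4 defines percent change per patient, with that patient's baseline as divisor. Section 7.1.7.2 applies it to SMBG weekly events and to CGM percent time, each at <70, <60 and <50 mg/dL. It "will also be summarized by the percent change from baseline by visit, cohort and RZ358 Total using descriptive statistics", and these include the mean, SD, SE, median, range and 95% CI for the mean.

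**Status of the endpoints.** Only SMBG <70 is listed as secondary in section 5.2. The lower SMBG thresholds fall under the exploratory item "Average weekly hypoglycemia incidence (event rate) at each of the specified glucose thresholds by SMBG", although section 7.1.7.2 calls all three secondary.

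**Entry floors.** Protocol 4.3 requires at least 3 "hypoglycemia events (<70 mg/dL) per week by SMBG and/or according to the" Investigator's evaluation. No readable SMBG criterion exists at <60 or <50. For CGM, amendment 5.0 requires at least 4% of time below 70 and at least three events below 50. SAP section 2.2 says that three Cohort 1 patients entered under amendment 4.0, whose CGM criterion concerned <70 only.

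**Missing values.** CGM and SMBG data are not imputed (section 4). Under section 3, the Missing statistic "will also be evaluated by enumerating the number of missing entries/patients". No readable text separates an undefined ratio from an absent value.

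**AOC.** Section 3 says that AOC and AUC "of glucose will also include coefficient of variation (CV %), Geometric Mean, Geometric CV". Section 7.1.7.3 lists "Geometric Mean, Geometric CV (%), Median, Minimum, Maximum and 95% CI for Geometric Mean" for them. Section 9.1.1 builds AOC as a sum of pieces below the threshold.

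**The concern.** A percent change cannot go below -100% but has no upper limit, so a few patients with low baselines can dominate a cohort of 6 to 8. A patient with a zero baseline drops out altogether and would look like a patient without data. The reported mean would then describe the baseline rate as much as the drug.

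For AOC the trouble comes from success. A patient whose glucose never falls below the threshold has AOC of exactly zero, and a geometric mean needs its logarithm. Dropping that patient removes the best possible response. Adding a constant lets the constant set the answer.

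At stake is how some secondary and exploratory rows are read. The primary endpoint (time in range 70-180 mg/dL), the absolute changes, and the arithmetic mean and median of AOC do not depend on either calculation.

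**Working it through.** **The plan's own figure.** The worked example in SAP 9.1.1 reproduces: AUC = 30 + 90 + 30 = 150 and AOC = 35 + 20 + 70 + 110 = 235 mg/dL·hr. It sums only deviations beyond the threshold, so a patient with no reading below 70 has AOC = 0.

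**SMBG with no floor.** Assumptions: the baseline count X is Poisson with mean m = rate × days/7, every patient has the same rate, and the baseline lasts 10 days. Rates are assumed because the documents give none.

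- Share undefined = exp(-m).
- Expected mean percent change among the rest = 100 × [(1 - reduction) × m × E(1/X given X>0) - 1].
- Example at 3/week: m = 3 × 10/7 = 4.286 and E(1/X) = 0.3064, so 4.286 × 0.3064 - 1 = +31%.

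| Rate/week | Undefined | Mean, no effect | Mean, true halving |
|---|---|---|---|
| 0.5 | 49% | -41% | -70% |
| 1 | 24% | -3% | -51% |
| 3 | 1% | +31% | -34% |
| 5 | 0.1% | +20% | -40% |
| 10 | 0% | +8% | -46% |

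The baseline window is not readable. With 7 or 14 days the no-effect means are -56% or -23% at 0.5/week, -23% or +15% at 1, +30% or +25% at 3, +29% or +13% at 5, and +13% or +6% at 10. If rates vary between patients (gamma, CV 0.7), the 10-day figure falls to about +19% at 3/week and rises to about +13% at 10/week.

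**The planned median** (simulated, 24 patients, no effect, 14-day end-of-treatment window) is -52% at 0.5/week, -24% at 1 and +2% at 3. It is sound only where zero baselines are rare.

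**One patient in a small cohort** (invented). Baselines are 1, 6, 7, 8, 10, 12, 14; later values are 4, 3, 3.5, 4, 5, 6, 7. Six patients change by -50% and one by +300%. The mean is 0% and the SD 132.3. The CI is 0 ± 2.447 × 132.3/√7, or -122% to +122%, and its lower limit is impossible. The median is -50%. The change of means is 4.64/8.29 - 1 = -44%.

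**The change of means, no floor, no effect, 10 days.** Its error is 100 × [M × E(1/S given S>0) - 1], with S Poisson and M = n × rate × 10/7. For 24 patients this gives +7%, +3%, +1% and +1% at 0.5, 1, 3 and 5/week. For 7 patients it gives +29%, +13%, +4% and +2%.

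**SMBG <70 where recorded SMBG met the floor** (X at least 3, 5 or 6 in 7, 10 or 14 days), no effect:

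| Rate/week | Planned mean, 7/10/14 days | Change of means |
|---|---|---|
| 3 | -22/-28/-19% | -28/-31/-22% |
| 5 | +3/-2/+4% | -9/-9/-4% |
| 7 | +12/+7/+7% | -2/-2/0% |
| 10 | +12/+8/+6% | 0/0/0% |

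No zero divisor arises here. At the lowest rates the error is regression to the mean, which neither statistic removes.

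**CGM percent time <50.** The event definition is blacked out, so assume 5 to 15 minutes per event. Three events in 7 days are then 15 to 45 of 10,080 minutes, or 0.15% to 0.45%. A rise of 6.4 minutes/day (6.4/1,440 = 0.44 points) would read as about +300% or +100%.

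**AOC with one zero** (invented: 40, 25, 18, 10, 6, 0). The arithmetic mean is 99/6 = 16.5. The geometric mean is 0 if the zero is kept, and the geometric CV and CI are undefined. It is 16.1 if the zero is dropped, and 4.7, 6.8 or 9.8 if 0.01, 0.1 or 1 is added and then subtracted. A zero requires no reading below threshold in 14 × 288 = 4,032 readings, or 14 × 96 = 1,344 overnight, so it is likeliest at <50 overnight. If 5% to 10% of patients had a zero (assumed), the chance of at least one, 1 - (1 - q)^n, is 26% to 57% in a cohort of 6 to 8 and 71% to 97% in 24 to 32 patients.

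**The case against.** **Redaction.** Blacked-out text follows both the percent-change definition and the SMBG rate definitions in SAP section 4, and a zero rule may lie there. It therefore cannot be said that the plan has none. Such a rule would settle the undefined values. It would not remove the dependence on baseline rate, or the dependence of a geometric mean on an added constant.

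**SMBG <70.** A reader might infer that percent change fails here too and should be replaced. The documents do not support this. The 3/week floor protects patients who met it on recorded SMBG, and for them the change of means has the larger error at both 3 and 5/week. Only patients who qualified on Investigator evaluation without 3/week on recorded SMBG are exposed, and their share is not given.

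**Size.** A reader might infer an error of tens of points at every low rate. At 1/week with a 10-day baseline it is only -3%. The figures rest on assumed rates, an unreadable window and, in the main table, identical patients.

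**The test.** Section 7.1.7.2 repeats the paired t-test sentence after percent change, so a reader might conclude that percent change is tested. Section 7.1.7.3 instead says that its parameter "is the mean difference in glycemic efficacy of CGM/SMBG parameters within cohort", and the table in 7.1.7.4 lists "Average weekly incidence, cohort" as the analysis variables. No error in the test is shown. The Wilcoxon fallback changes the test only, not these descriptive rows.

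**Importance.** The study is not powered, and Protocol 7.1 treats CIs and p-values as hypothesis generating. Median, absolute change and arithmetic AOC summaries are already planned. This stands, and is why the point is minor.

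**Conclusion.** The concern holds in limited form. For SMBG <60 and <50, the planned mean and CI of individual percent change have no readable protection against zero or low baselines. Under the stated Poisson assumptions with a 10-day baseline, the no-effect mean runs from about -41% to +31% across 0.5 to 3 events/week, and up to about half of patients have no value. The true size and sign cannot be known from the documents. SMBG <70 is affected only for an unknown share of patients. CGM percent time <50 is non-zero at entry under amendment 5.0 but may have a very small divisor; the three amendment 4.0 patients had no <50 criterion.

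The AOC point needs no rate assumption: one zero value is enough to break the geometric row for its cohort and for RZ358 Total. How often that occurs is unknown.

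Severity is minor. Nothing here touches the primary endpoint, the absolute changes, or the arithmetic mean and median of AOC.

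**What to change.** 1. In SAP 7.1.7.2, for SMBG <60 and <50, replace the mean, SD, SE and CI of individual percent change with 100 × (mean at visit / mean at baseline - 1), in patients with both values and with zero baselines included. Give a patient-level bootstrap 95% CI for RZ358 Total only. Where a cohort has very few baseline events, show the two means without a percentage, and set the limit in advance. At an expected 20 baseline events, for example, the no-effect error is about +6% (20 × 0.0528 - 1).
2. For SMBG <70 and CGM percent time <50, keep the planned rows but lead with the absolute change and the median percent change. Leave CGM percent time <70 and <60 as written.
3. Throughout, count undefined values (zero baseline) separately from Missing. Note that the median percent change is unreliable where zero baselines are common.
4. In sections 3 and 7.1.7.3, drop the geometric mean, geometric CV and its CI for AOC. Rely on the planned arithmetic mean with CI and the median, and add the number of zeros. AUC above threshold may keep geometric statistics for actual values.
5. If a redacted zero rule exists, cite it in 7.1.7.2 and 7.1.7.3.

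The cost is SAP wording and a little programming. The change of means gives more weight to patients with many events, and it is itself skewed in a cohort of 6 to 8 at 1 event/week or less.
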